5.5 Study Product Accountability Procedures

Records of the disposition of the investigational agent, including the date and quantity of the drug received, to whom the drug was dispensed (participant-by-participant accounting), and a detailed accounting of any drug accidentally or deliberately destroyed will be kept by the study investigators.

Records for receipt, storage, use, and disposition will be maintained by the investigator. A drug-dispensing log will be kept current for each participant. This log will contain the identification of each participant and the date and quantity of drug dispensed.

5.6 Concomitant Medications and Procedures

All concomitant prescription medications taken during study participation will be in Clinical Research Information Management System of the NIAID (CRIMSON). For this protocol, a prescription medication is defined as a medication that can be prescribed only by a properly authorized/licensed clinician. Medications to be reported in CRIMSON are concomitant prescription medications, over-the-counter and non-prescription medications taken at the time of AEs (all grades).

5.7 Drug Interactions

All medications will be reviewed by the study team to identify any potential drug interactions.

Magnesium sulfate

It has been reported that magnesium may reduce the antibiotic activity of streptomycin, tetracycline and tobramycin when administered together.

Central nervous system (CNS)—When barbiturates, narcotics or other hypnotics (or systemic anesthetics) are given in conjunction with magnesium, their dosage should be adjusted with caution because of the additive CNS depressant effects of magnesium. CNS depression and peripheral transmission defects produced by magnesium may be antagonized by calcium.

Neuromuscular blocking agents—Excessive neuromuscular block has occurred in subjects receiving parenteral MgSO₄ and a neuromuscular blocking agent; these drugs should be administered concomitantly with caution.

Cardiac glycosides—MgSO₄ should be administered with extreme caution in subjects undergoing digitalis, because serious changes in cardiac conduction resulting in heart block may occur if administration of calcium is required to treat magnesium toxicity.

6 Study Schedule

All study visits will take place at the NIH Clinical Center. A schedule of procedures is attached as Appendix B.

6.1 Screening/Enrollment (Week -5 to baseline)

Informed consent may take place at the Clinical Center or by telephone prior to the patient's arrival (see Section 13.1.2). Patients will undergo the following procedures:

- Medical history and physical examination
- Low radiation x-ray computed tomography (CT) scan to include neck, chest, abdomen, and pelvis if not done in the last 6 months
- Electrocardiogram (EKG)
- Instructions for starting a 2-week washout of all magnesium-containing supplements will be discussed during informed consent

Clinical laboratory evaluations:

- Complete blood count [CBC] with differential
- Acute care panel, mineral panel, hepatic panel
- HIV test (if not done within 1 year)
- EBV by PCR
- Cytomegalovirus (CMV) by PCR
- EBV FISH (research assay)

6.2 Baseline visit after 2 week washout period (Day -3 to Day 0):

At the end of the washout period, patients will be queried regarding recent supplement use, medications and medical history will be reviewed, and a physical exam will be performed.

Depending on which cohort subjects are assigned to, a baseline NKG2D expression on CD8 T cells and NK cells by flow cytometry or EBV FISH and EBV viral load will be determined from blood drawn on at least 3 consecutive days and averaged.

Clinical laboratory evaluations:

- 24-hour urine collection for magnesium
- CBC with differential
- Acute care, mineral and hepatic panels
- Quantitative immunoglobins
- Lymphocyte phenotyping
- Prothrombin time/partial thromboplastin time (PT/PTT)
- CMV by PCR
- EBV by PCR (will be drawn on 3 consecutive days, cohort 1)
- Erythrocyte sedimentation rate (ESR)
- C-reactive protein (CRP)
- Total and ionized serum magnesium

Research assays

- Intracellular free Mg²⁺
- EBV FISH (will be drawn on 3 consecutive days, cohort 1)
- RNA extraction
- NKG2D expression on CD8 T cells and NK cells by flow cytometry (will be drawn on 3 consecutive days, cohort 2)
- Storage of serum, plasma and peripheral blood mononuclear cells (PBMCs)

At the conclusion of the baseline visit, patients will be provided oral study agent (magnesium L-threonate or placebo), instructions for taking it, and a medication log for recording AEs (Appendix C). The medication log will contain the study drug dosing information and will be used as a memory aide to collect information the subject would like to recall.

6.3 Part I: Oral study agent (Week 1 to Week 24)

Oral magnesium or placebo (Week 1 to Week 12)

On Day 0, patients will begin to self-administer the oral study agent according to the dose escalation scheme in section 5.4.2.

Dose escalation every 2 weeks (Weeks 2, 4, and 6, or until maximum tolerated dose is reached)

Prior to increasing the study drug dose the study staff will contact patients to review their medication administration, assess for AEs and approve escalation to the next dose. In addition, patients will be contacted 1 week after dose escalation to assess for AEs.

4-week follow-ups (Weeks 4 and 8 +/- 1 week)

Patients will come to NIH for clinical and research evaluations to include:

- Medical history and physical exam

Clinical laboratory evaluations:

- CBC with differential
- Acute care panel, mineral panel, hepatic panel
- EBV by PCR
- CMV by PCR
- CRP
- ESR
- Total and ionized serum magnesium
- TBNK
- Spot urine magnesium

Research assays:

- Intracellular free Mg²⁺
- EBV FISH
- RNA extraction
- NKG2D expression on CD8 T cells and NK cells by flow cytometry
- Storage of serum, plasma, and PBMCs

Week 12 (+/- 1 week)

At the conclusion of 12 weeks of study agent patients will return to NIH for the following evaluations:

- Medical history and physical exam
- EKG

Clinical laboratory evaluations:

- 24-hour urine collection for magnesium
- CBC with differential
- Acute care, mineral and hepatic panels
- Quantitative immunoglobins
- Lymphocyte phenotyping
- CMV by PCR
- EBV by PCR
- ESR
- CRP
- Total and ionized serum magnesium

Research assays:

- Intracellular free Mg²⁺
- EBV FISH
- RNA extraction
- NKG2D expression on CD8 T cells and NK cells by flow cytometry
- Storage of serum, plasma, and PBMCs

Crossover (Week 13-24 +/- 1 week)

To crossover (from magnesium supplementation to placebo or from placebo to magnesium supplementation), patients will return any unused study agent and begin dose escalation with a new oral agent (magnesium or placebo). Patients will be provided dosing instructions and a medication log for recording AEs (Appendix C).

Dose escalation every 2 weeks (2, 4, and 6 weeks after the start of crossover, or until maximum tolerated dose is reached)

Prior to increasing the study drug dose staff will contact patients to review their medication administration, assess for AEs and approve escalation to the next dose. In addition, patients will be contacted 1 week after dose escalation to assess for AEs.

Follow-up visits:

Patient will come to NIH at Weeks 16 and 20 for the same clinical and research evaluations as Weeks 4 and 8.

Week 24 (+/- 1 week)

At the end of 24 weeks, patients will repeat all the evaluations that were performed at the end of Week 12. This will be the last visit for patients who do not continue to Part II. Part II will be conducted only among patients in whom oral magnesium is not more effective than placebo.

6.4 Part II: Intravenous MgSO₄ plus oral magnesium (Weeks 25-50 +/-2 weeks)

6.4.1 Washout period (Week 25 to Week 26 +/-2 weeks)

Patients proceeding to Part II will stop taking the study agent and refrain from all magnesium-containing supplements for at least 2 weeks.

6.4.2 IV infusion (Week 27 +/-2 weeks)

Patients participating in Part II will be admitted to the inpatient ward at the NIH Clinical Center to complete the following procedures between 1 and 2 days prior to initiating infusion:

- Medical history and physical exam
- EKG

Clinical laboratory evaluations:

- Spot urine magnesium
- CBC with differential
- Acute care, mineral and hepatic panels
- Quantitative immunoglobins
- Lymphocyte phenotyping
- PT/PTT
- CMV by PCR
- EBV by PCR
- ESR
- CRP
- Total and ionized serum magnesium

Research assays:

- Intracellular free Mg²⁺
- EBV FISH
- RNA extraction
- NKG2D expression on CD8 T cells and NK cells by flow cytometry
- Storage of serum, plasma and peripheral blood mononuclear cells (PBMCs)

Patients will remain hospitalized to receive IV MgSO₄ for 3 days. The daily dose of 30 mg/kg will be divided and infused 3 times per day (every 8 hours). During this period, patients will have a daily physical exam, be assessed for AEs, and undergo the following procedures:

12 hours (+/- 3 hours) after infusion initiation

- EKG

24 hours and 48 hours (+/- 3 hours) after infusion initiation

- Begin 24-hr urine collection 48 hours after starting IV magnesium
- EKG

Blood will be drawn for the following studies:

- CBC with differential, acute care, mineral and hepatic panels
- Total and ionized serum magnesium
- Intracellular free Mg²⁺
- NKG2D expression on CD8 T cells and NK cells by flow cytometry

Upon completion of the last IV magnesium infusion:

- EKG

Clinical laboratory evaluations:

- CBC with differential
- Acute care, mineral and hepatic panels
- Quantitative immunoglobins
- Lymphocyte phenotyping
- CMV by PCR
- EBV by PCR
- ESR
- CRP
- Total and ionized serum magnesium

Research assays

- Intracellular free Mg²⁺
- EBV FISH
- RNA extraction
- NKG2D expression on CD8 T cells and NK cells by flow cytometry
- Storage of serum, plasma, and PBMCs

6.4.3 Oral magnesium (open label) (Week 27-Week 50 +/- 2 weeks)

Following 3 days of infusion, patients will be discharged with a supply of oral magnesium L-threonate with instructions to begin taking the supplements and to escalate the dose every 2 weeks. Once patients reach the maximum planned dose or highest tolerated dose from Part I, they will continue that dose for the remainder of the study (24 weeks post-infusion). A medication log will be provided to record AEs and missed doses. The medication log will contain the study drug dosing information and will be used as a memory aide to collect information the subject would like to recall. Patients will return to the Clinical Center at 12 week intervals (weeks 38 and 50) after the start of oral supplementation for serum magnesium evaluation and tolerance assessment, as in Part I (see 12-week follow-ups, above).

At Week 38, patients will repeat the procedures and blood evaluations conducted at Week 12 of Part I.

6.4.4 End-of-study follow-up (Week 50 +/- 2 weeks)

- Medical history and physical examination
- 24-hour urine collection for magnesium
- Blood will be drawn to repeat the evaluations listed under Week 12 of Part I.
- EKG

7 Study Procedures and Evaluations

Medical history and physical examination: Each subject will be queried regarding their medical history, have vital signs and weight measured and have a physical examination. Assessment of medical history will include queries regarding missed attendance at school or work and emergency room visits since the last study visit, in addition to recent infections and other clinical manifestations (eg, rash, warts, etc.). Complete physical examinations will be conducted at enrollment and the post-study follow-up. Complaint-targeted examinations will be conducted at the other study visits. A pediatric consult will be obtained for all patients under the age of 18 years.

Phlebotomy: Blood will be collected for routine serologic, hematologic, and clinical chemistry evaluations (as described in section 6) as well as laboratory evaluations including flow cytometry/EBV FISH, EBV PCR, quantitative serum immunoglobins, lymphocyte phenotyping and intercellular free Mg²⁺. EBV FISH will not be performed for EBV-naïve subjects.

24-hour urine collection: The 24-hour urine Mg²⁺ test will involve collecting all urine passed during a 24-hour period. Patients will be instructed to start the 24 hr urine by urinating directly in the toilet. After urination, the time and date should be written on the container. All urine should be saved for the next 24 hours in the supplied container on ice or in a cooler. Exactly 24 hrs after the start of the test the patient should void one last time and collect the specimen. This time and date should be recorded on the container.

EKG will be performed to rule out electrical cardiac abnormalities and ensure continued eligibility to receive magnesium supplementation. A cardiologist on the study staff will address any cardiac abnormalities.

CT scan: A CT scan of the neck, chest, abdomen and pelvis will be performed on all patients to assess lymphoproliferative disease. Oral and IV contrast will be used, except in patients known to have had a reaction to IV contrast media or poor venous access. Patients will be instructed to fast for 4 hours prior to CT scan. If lymphoma is detected, patients will be referred for treatment.

Patient medication log (Appendix C) will be completed by patients to document any adverse effects of the study agent along with evaluation of drug adherence.

8 Potential Risks and Benefits

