A Double-blind, Placebo-controlled, Crossover Study of Magnesium Supplementation in Patients with XMEN Syndrome

NIAID Protocol Number: 15-I-0161

Sponsored by: NIAID

Version Number: 9.0

Date: March 8, 2019

Principal Investigator: [name]

Study Staff Roster

Principal Investigator:

[name] Laboratory of Immunology (LI)/NIAID

Associate Investigators:

[name] LI/NIAID

[name] Laboratory of Host Defenses/NIAID

[name] LI/NIAID

[name], ScM, CGC LI/NIAID

[name] National Heart Lung and Blood Institute/
Cardiovascular and Pulmonary Branch

[name] Biostatistics Research Branch/NIAID

Study Coordinator:

[name] LCID/NIAID

Medical Advisory Investigator:

[name] LID/NIAID

Protocol Summary

Full Title:	A double-blind, placebo-controlled, crossover study of magnesium supplementation in patients with XMEN syndrome
Short Title:	XMEN syndrome and magnesium
Clinical Phase:	Phase 1 and 2
Conducted by:	NIAID/LI
Principal Investigator:	[name]
Sample Size:	n=20 (n=10 for each cohort)
Accrual Ceiling:	n=30
Study Population:	Patients \geq 6 years with X-linked immunodeficiency with magnesium defect and increased susceptibility to Epstein-Barr virus (EBV) infection and neoplasia (XMEN) syndrome. Subjects will be divided into 2 cohorts: Cohort 1 (high EBV): Subjects with baseline blood EBV viral load \geq 5,000 copies/mL or EBV log \geq 3.7 IU/mL. Cohort 2 (low/no EBV): Subjects with baseline blood EBV viral load <5,000 copies/mL or EBV log <3.7 IU/mL.
Accrual Period:	4 years
Study Design:	A randomized, double-blind, placebo-controlled, crossover study to evaluate the safety and efficacy of oral magnesium L-threonate in subjects with XMEN syndrome. In Part I, patients within each cohort will be randomized into 2 arms. Each arm will receive 12 weeks of either oral magnesium L-threonate or placebo followed by crossover treatment for another 12 weeks. Patients in cohort 1 who experience \geq 0.5-log reduction in the number of EBV-infected B cells and patients in cohort 2 who experience \geq 2-fold increase in NKG2D receptor expression on CD8 T cells during oral magnesium treatment as compared to placebo will have completed the study. Patients who do not meet these respective criteria will undergo a 2-week washout and transition to Part II in which they will be hospitalized to receive 3 days of IV MgSO ₄ . These patients will then restart escalating doses of oral magnesium and continue for 24 weeks, at which point participation will be complete.

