3.2 Study Endpoints

Primary Endpoints

- Cohort 1: Difference between the absolute number of EBV-infected B cells (by EBV FISH) after 12 weeks of oral magnesium supplementation and after 12 weeks of placebo.
- Cohort 2: Difference between NKG2D expression in CD8 T cells after 12 weeks of oral magnesium supplementation and after 12 weeks of placebo.

Secondary Endpoints

- Incidence and severity of AEs throughout the study.
- Contingent upon patient participation in Part II, differences in EBV viral load and number (or percent) of EBV-infected B cells (cohort 1) or NKG2D expression in CD8 T cells (cohort 2) by duration (12 weeks of IV+oral versus 24 weeks of IV+oral) of magnesium supplementation regimen.
- Change in the intracellular pool of free Mg²⁺ by duration of magnesium supplementation regimen.
- Change in NKG2D expression in cohorts 1 and 2.

Exploratory Endpoints

- Change in CD4 T cell counts, B cell counts (or percent), and/or in NKG2D expression on NK (CD3-CD56+) cells.
- Quantification of EBV-infected B cells as determined by flow cytometry and FISH.
- Percent of anemia, neutropenia, thrombocytopenia, and abnormal liver enzymes.
- Difference in number and severity of infections between placebo and magnesium treatment periods.
- Difference in number of health-related days of missed school/work between placebo and magnesium treatment periods.
- Difference in number of emergency room visits and hospital admissions between placebo and magnesium treatment periods.

4 Study Population

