4.2 Subject Inclusion Criteria

All of the following inclusion criteria must be met prior to enrollment:

1. Molecular diagnosis of the MAGT1 genetic defect
2. ≥6 years years of age

3. Willingness to stop magnesium supplements (other than the study agent) and any multivitamins or over-the counter-supplements that may contain magnesium for the duration of the study
4. Willingness to go without magnesium supplementation during a 12-week placebo period and during both 2-week washout periods (pre-study and mid-study)
5. Willingness to have samples stored for future research
6. Must have a physician at home for follow-up care

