13.3 Sample Size Justification

For cohort 1, the primary endpoint is the difference between the absolute number of EBV-infected B cells (EBV FISH) after 12 weeks of magnesium supplementation and after 12 weeks of placebo. With 10 subjects, there is 90% power to detect 1.15 standard deviation change by the 2-sided paired *t*-test with type I error rate of 0.05. To evaluate EBV change over time, we will compare the absolute number of EBV-infected B cells at the end of the control period and at the end of the treatment period. We will report the mean change in EBV with 95% confidence intervals.

For cohort 2, the primary endpoint is the difference between the MFI for NKG2D surface expression on CD8+T cells after 12 weeks of magnesium supplementation and after 12 weeks of placebo. With 10 subjects, there is 90% power to detect 1.15 standard deviation change by the 2-sided paired *t*-test with type I error rate of 0.05. To evaluate NKG2D change over time, we will compare the MFI for NKG2D surface expression on CD8+ T cells at the end of the control period and at the end of the treatment period. We will report the mean change in NKG2D with 95% confidence intervals.

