13.6 Randomization within each cohort

Patients will be allocated to Arm 1 or Arm 2 using a permuted block design with block size of 20. This means that exactly 10 patients will be randomly assigned to each arm. The study statistician will provide the randomized list of arm assignments.

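### Missed school or work is compared as a raw count of days with no record of scheduled days, so school holidays cost this exploratory comparison precision

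*Combined protocol and SAP*

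**What the plan says.** Section 3.2 and the Protocol Summary list the exploratory endpoint as "Difference in number of health-related days of missed school/work between placebo and magnesium treatment periods". It is a count, with no rate, denominator or offset.

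Section 7, under medical history and physical examination, says the history will include "queries regarding missed attendance at school or work and emergency room visits since the last study visit", together with recent infections and other clinical manifestations. Appendix B schedules a medical history at baseline and at Weeks 4, 8, 12, 16, 20 and 24.

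The Protocol Summary sets the design: "Each arm will receive 12 weeks of either oral magnesium L-threonate or placebo followed by crossover treatment for another 12 weeks". Section 6.3 allows a window of one week either side at Weeks 12 and 24. Section 4.2 admits patients at "≥6 years years of age". The planned size is 20, with 10 per cohort.

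Section 13 covers the primary endpoints, the Part II decision and the Part II secondary analyses. It contains no analysis of missed school or work.

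**The concern.** A crossover removes stable differences between patients. It does not equalise the opportunity to miss a day, which depends on the calendar. A pupil cannot miss school in a holiday, and the two periods fall in different parts of the year. A raw difference therefore mixes any magnesium effect with the difference in days at risk.

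Two smaller gaps add to this. The endpoint is restricted to health-related absence, but the query as described is not. The visit windows also let period 1 run 11 to 13 weeks and period 2 run 10 to 14 weeks, so raw counts vary with period length even for adults in steady work.

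At stake is the precision of one of the few patient-experienced outcomes in a trial whose primary endpoints are laboratory measures. Scheduled days are hard to reconstruct reliably afterwards.

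**Working it through.** **The plan's own figure.** Section 13.3 states: "With 10 subjects, there is 90% power to detect 1.15 standard deviation change by the 2-sided paired" *t*-test. With noncentrality 1.15 × √10 = 3.64 and 9 degrees of freedom, power is 0.898. All six rows of Table 3 give 0.897 to 0.902, so the table reproduces. It covers only the primary endpoints; no figure is given for missed days.

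**Inputs.** From the documents: two consecutive 12-week periods, 10 patients per cohort, 20 in total, age 6 or over. Assumed, because the documents do not give them: 5 scheduled days a week (60 per full period), 10% of days missed on placebo, and a magnesium/placebo rate ratio ρ of 0.5 to 0.8.

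**One patient.** Expected missed days = daily rate × scheduled days. With a holiday of h weeks in the placebo period only, the raw difference (magnesium minus placebo) is 0.10 × [60ρ − (60 − 5h)]. It turns positive, the wrong sign, when h > 12(1 − ρ): more than 2.4, 3.6 or 6 weeks for ρ = 0.8, 0.7 or 0.5.

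At 10% v 7% missed:

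| Holiday | Raw difference (days) |
|---|---|
| None | 4.2 − 6.0 = −1.8 |
| 4 weeks, placebo period | 4.2 − 4.0 = +0.2 |
| 8 weeks, placebo period | 4.2 − 2.0 = +2.2 |
| 8 weeks, magnesium period | 1.4 − 6.0 = −4.6 |

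Missed days per scheduled day differ by −3 percentage points in every row.

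**Ten patients sharing an 8-week holiday in period 2.** With a 5:5 sequence split the expected mean is (2.2 − 4.6)/2 = −1.2 days: attenuated from −1.8, sign kept. With 7:3 in favour of magnesium first it is (7 × 2.2 − 3 × 4.6)/10 = +0.16. Section 13.6 states: "Patients will be allocated to Arm 1 or Arm 2 using a permuted block design with block size of 20". If a cohort's 10 patients are the first half of such a block, a split of 7:3 or worse has probability 17.9%, of which 8.9% is in the reversing direction.

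Simulated power for this shared-holiday case (20,000 trials, two-sided 0.05):

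| Rate ratio, holiday | Raw count | Rate |
|---|---|---|
| 0.5, none | 79% | 79% |
| 0.5, 8 weeks | 19% | 51% |
| 0.7, none | 36% | 36% |
| 0.7, 4 weeks | 21% | 30% |

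In the 8-week case, 79 − 51 = 28 points are lost because there are fewer days at risk, and no analysis recovers them. The other 51 − 19 = 32 points are recoverable with a denominator.

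**Staggered starts.** Assume 38 school weeks, an 11-week summer break, two winter weeks and one spring week. Over the 52 possible start weeks, 40% give periods that differ by at least 20 scheduled days and 21% by at least 40 (worst case 5 v 60). Approximate simulated power, with Poisson missed days, gamma between-patient variance 0.5 and 10% v 5% missed, comparing a paired *t*-test on raw days with an exposure-weighted test on rates:

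| Patients | Pupils | Raw count | Rate |
|---|---|---|---|
| 10 | all | 35% | 52% |
| 10 | half | 52% | 62% |
| 20 | all | 71% | 90% |
| 20 | half | 88% | 95% |

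Repeat runs moved these figures by up to about four points. One-sided false-positive rates stayed near nominal for both tests, at about 2–3%. The raw group mean was zero or wrong-signed in about 3% of trials with 10 patients, all pupils.

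**The case against.** The strongest reply is that little hangs on this. The endpoint is one of six exploratory ones, it is unpowered, and it triggers no decision: Part II entry rests on EBV FISH or NKG2D. Infections, emergency visits and admissions are compared over the same periods and need no school timetable. All of that stands and limits the weight of the point.

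Second, the paired *t*-test on raw days is an assumed method, since section 13 names none. That also stands, but an unstated analysis does not supply the missing denominator.

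Third, a reader might infer that the trial never asks about scheduled days or the reason for absence. The documents do not support that. Section 7 is a one-sentence summary inside a medical history, the data collection form is not included, and the content of Appendix C is not shown. What can be said is that the protocol describes neither item.

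Fourth, a reader might infer that holidays bias the comparison or are likely to reverse the trial's result. They do not bias it on average, because order is randomized. Reversal is mainly a single-patient effect: reversing the expected group mean in the example above takes a long holiday shared by all patients plus an unbalanced split, and accrual over four years would dilute a shared calendar. Wrong signs are commoner for smaller effects (16% for the raw count v 9% for the rate at 10% v 7%, 10 patients, all pupils), but part of that is ordinary small-sample noise.

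Fifth, the gain depends on inputs the documents do not give. The endpoint is not defined by cohort, so 20 patients is a natural analysis set; with half pupils the gain is then about 7 points. At 5% v 3.5% missed with 10 patients, all pupils, power is 11% v 14%, inadequate either way. At 10% v 7% with 20 patients, all pupils, it is 30% v 47%.

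Last, a rate can select on health, because a patient too ill to be enrolled or employed has no scheduled days. This is a fair criticism of a bare rate, and the change below has to deal with it.

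**Conclusion.** The point holds as a modest one about measurement. The endpoint is a raw count, the described query carries no scheduled days and no health restriction, and nothing in section 13 repairs this. The consequence is attenuation and lost precision in an exploratory comparison, without average bias. Under the assumed calendar with 10% v 5% missed, the power forgone is about 17 points with 10 patients who are all pupils (52 − 35) and about 7 points with 20 patients of whom half are pupils (95 − 88). These sizes rest on assumed school calendars, absence rates, age mix and test. The need for a denominator and the mismatch over health-related absence do not. The primary endpoints and the Part II decision are untouched.

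**What to change.** At each Part I visit, record since the last visit (a) days scheduled for school or work and (b) days missed for health reasons.

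Define the endpoint as health-related missed days per scheduled day. Compare it within patient between the magnesium and placebo periods, weighted by scheduled days or with a count model using log scheduled days as offset, and include a period term. Report the raw count alongside.

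Treat a period with no scheduled days because of holiday as not evaluable, not as zero. Where the patient was not enrolled or not working because of illness, record that reason and count the days that would otherwise have been attended as both scheduled and missed, so that the sickest patients are not selected out.

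The cost is one added question and the reason for absence, at visits that already take this history, plus a short analysis paragraph. A few patients may not contribute to this exploratory comparison. No visit, procedure or blood draw is added.
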